Connecticut Children's Sports Physical Therapy and Elite Sports Medicine have a long relationship of working collectively with the management of patients with ACL tears both surgically and with rehabilitation post-surgically. The current standard of care for the rehabilitation of ACL injuries includes several interventions and the process can last up to 12 months. The early phases of rehabilitation include the use of therapeutic exercise, manual therapy and modalities to help reduce pain, normalize range of motion and gait. In the later phases, a progressive lower extremity strengthening program is completed, in addition to plyometric and jump training. Finally, Standardized strength assessments at 3 months' post-operative, and return to sport test between 6 and 9 months are used to help physical therapists and surgeons in clinical decision making for progression with functional and recreational activities. Since early 2019, BFR training has been implemented consistently for post-operative patients at Connecticut Children's Sports Physical Therapy that have undergone ACL reconstruction, as well as patellar and shoulder stabilization procedures.

While there are a number studies that have reported on the use of BFR in the adult population [14], there is limited information about the use of BFR in the adolescent population. This study aims to

evaluate the use of BFR training in conjunction with traditional ACL reconstruction rehabilitation in adolescents.

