## Purpose of the Research, Specific Aims and Hypotheses

The purpose of this study is to determine the safety and efficacy regarding the addition of BFR-based exercise to traditional methods of physical therapy in the adolescent, post-surgical population.

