### Secondary aim:

- 1. To determine the impact of adding BFR training during post-surgical rehabilitation on patient reported outcomes.
  - a. We hypothesize that BFR training will show greater patient reported outcome scores on the post-op when compared to a control group.
- 2. To determine the impact of adding BFR training during post-surgical rehabilitation on hypertrophy and mid-thigh circumference.
  - a. We hypothesize that BFR training will demonstrate significant increased mid-thigh circumference over measured time points.
- 3. To determine and record patient tolerance and reported side effects and to BFR training during postsurgical rehabilitation.
  - a. We hypothesize that patient tolerance to BFR will be consistent with previously published literature.

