### Exclusion criteria for study group and prospective controls:

- a. Specific exclusions
  - Patients older than 18 and younger than 12 at the time of surgery
  - Any additional diagnoses or deformity not related to knee injury that could affect knee strength
- Additional lower extremity injury at time of knee injury (e.g., ankle injury) requiring treatment Previous surgical intervention on the knee (ipsilateral and contralateral)

Patients with weight bearing restrictions for greater than two weeks after surgery due to concomitant pathology such as meniscal root/radial repair, chondral pathology, or multi-ligament pathology. Generic exclusion: "Subjects not meeting all inclusion criteria."

The exclusion of age is to ensure that the study population is old enough to complete testing on the HUMAC isokinetic dynamometer and young enough to be treated by one of our Elite Sports Medicine physicians.

The secondary diagnosis and previous knee injury exclusions are to limit the influence of other diagnoses or injuries on measured knee strength, as well as provide a more homogeneous group for comparison to past data.

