### Identification and Recruitment:

Once identified as a potential candidate, the study purpose and protocol will be explained and a brief summary of the study will be provided at the conclusion of the pre-operative appointment. Patients must meet all the requirements of inclusion and exclusion criteria to be eligible for consent.

Consent: Consent will take place at the pre-operative visit. The patient/parent will be given a detailed description of the purpose and methodology for this study. They will have the opportunity to read the consent forms and ask any questions they may have about the research. If they agree to participate, they will be asked to sign the consent form and a copy will be provided.

If patients agree to enroll, all demographics and information listed in the protocol will be stored in a data collection sheet that is listed in the attachments. This sheet will be used to record all pertinent information for all active participants on the study and stored in a secure folder on the G drive.

Retention: Eligible patients will be required to be seen for a minimum of 90% of patient visits to be included in this study.

**Retrospective control**: Patients that will be used as part of the retrospective control will be collected using a billing run with CPT codes related to ACL reconstruction from January 2017- January 2019.

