## Data Analysis:

The endpoint of this study is when data is collected and analyzed from 20 patients who have completed a one year follow up from date of surgery.

Data will be collected on all patients who meet the inclusion criteria for this study and have agreed to participate through the consenting process. Descriptive statistics will be completed to help gain an overall understanding of the data for the effect of BFR training on lower extremity strength, mid-thigh circumference and outcome measures. T-tests between strength and outcome variables for the BFR and non-BFR group to test if there are differences between the two groups. Correlation tests will be used to determine association between lower extremity strength and BFR training. Corrections will be made for multiple comparisons.

We will be entering into a Data Use Agreement with University of Connecticut (UCONN) for assistance with data analysis and interpretation as well as statistical analysis. All data sharing procedures will be in accordance with Connecticut Children's policy. All data will be de-identified prior to sharing to assure patient's confidentiality. The UCONN collaborator is not engaged in human subject research (no access to identifiers) and will obtain an independent determination from the UCONN IRB.

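### The 90% attendance condition has no exemption for safety and tolerance, so patients who stop attending because of BFR side effects would not be counted

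*Combined protocol and SAP*

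**What the plan says.** The attendance rule is in Identification and Recruitment, under Retention: "Eligible patients will be required to be seen for a minimum of 90% of patient visits to be included in this study". It does not appear in either list of inclusion criteria. Nothing says which visits form the denominator. Three readings are open:

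- the BFR sessions of the Proposed Protocol, two per week through week 12;
- all physical therapy visits, where the Background says of rehabilitation that "the process can last up to 12 months";
- the scheduled assessments: pre-operative, 3 months, return to sport and 12 months in person, with a 2-year contact by phone or email.

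The stated purpose is to "determine the safety and efficacy regarding the addition of BFR-based exercise" in adolescents after surgery. Secondary aim 3 begins "To determine and record patient tolerance and reported side effects". The Proposed Protocol has ability to complete recorded after each exercise, and side effects entered in the chart after each session. The Data Analysis section plans "T-tests between strength and outcome variables for the BFR and non-BFR group to test if there are differences between the two groups", together with descriptive statistics and correlations for strength, thigh circumference and outcome measures. It gives no tolerance summary, no denominator for one, and no all-treated or safety set.

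**The concern.** A tolerance estimate has to count the patients who could not tolerate the treatment. Here membership of the study depends on attendance after treatment has begun, and side effects are one plausible reason for not attending. Someone who leaves in week 3 because of pain under the cuff would fail the rule if BFR sessions or therapy visits are counted, and also if assessments are counted and that patient does not return for them. The patients most informative about tolerance could therefore be absent from its denominator and its numerator.

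Safety is named beside efficacy in the purpose, and the Background says that "there is limited information about the use of BFR in the adolescent population". The control group receives no BFR, so a comparison with it cannot reveal that BFR leavers were dropped. The Patient confidentiality statement has the data set frozen and names and record numbers removed once collection ends. After that, tracing a leaver's chart is harder.

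**Working it through.** The documents attach no calculation to the 90% rule, so there is no stated figure to reproduce. Two separate questions can be checked: what the rule could do to a tolerance rate, and how many patients it could remove.

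**1. Effect on the tolerance rate**

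Input from the plan: 33 BFR patients (Study Design). The number intolerant and the number who leave are assumptions.

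- All treated patients counted: 7/33 = 21.2%.
- Three of the 7 leave and no one else is removed: (7 − 3)/(33 − 3) = 4/30 = 13.3%.

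More generally, let p be the true intolerance rate, f the share of intolerant patients removed and a the share of tolerant patients removed:

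observed rate = p(1 − f) / [p(1 − f) + (1 − p)(1 − a)]

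| a | f | p = 10% | p = 20% | p = 30% |
|---|---|---|---|---|
| 0.10 | 0.50 | 5.8% | 12.2% | 19.2% |
| 0.10 | 0.25 | 8.5% | 17.2% | 26.3% |
| 0.10 | 0.10 | 10.0% | 20.0% | 30.0% |
| 0.10 | 0 | 11.0% | 21.7% | 32.3% |

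Example for row 1, p = 20%: 0.20 × 0.50 = 0.10; 0.80 × 0.90 = 0.72; 0.10/0.82 = 12.2%.

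The direction depends on who is removed. Tolerance looks too good only if intolerant patients are removed more often than tolerant ones (f > a). Equal removal leaves the rate unchanged, and removal of tolerant patients only overstates intolerance.

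**2. How many patients the rule removes under each reading of visits**

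Minimum attended = 0.90n, rounded up.

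- BFR sessions: n = 2 × 12 = 24. 0.90 × 24 = 21.6, so 22 are needed and at most 2 may be missed.
- Therapy visits: n = 60 is an assumption. 54 are needed.
- In-person assessments: n = 4. 0.90 × 4 = 3.6, so all 4 are needed. Consent is taken at the pre-operative visit, so everyone who consents has attended that one, and only the 3 post-operative visits are at risk.

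Assume visits are independent with the same true attendance q for every patient. Exclusion is the binomial probability of attending fewer than the minimum; for the assessments it is 1 − q³.

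| Reading | q = 95% | q = 92% | q = 90% |
|---|---|---|---|
| 24 BFR sessions | 12% | 30% | 44% |
| 60 therapy visits (assumed) | 3% | 20% | 39% |
| 3 post-operative assessments | 14% | 22% | 27% |

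Example: 1 − 0.95³ = 1 − 0.857 = 14%.

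At 95% attendance the choice of definition alone moves exclusion from 3% to 14%. This model gives tolerant and intolerant patients the same attendance, which is the equal-removal case in part 1. The second table therefore shows loss of sample, not tolerance bias.

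**The case against.** The strongest reply is that nothing is lost. Side effects and inability to complete are charted as treatment proceeds, no section says that leavers' records are deleted, and Secondary aim 3 is to determine and record, for which the recording is in place. No section explicitly applies the 90% rule to aim 3. The rule may have been meant only for efficacy, where a comparison among adherent patients is a legitimate choice in a small non-randomised pilot.

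Much of this stands. The gap is in who is counted, not in what is recorded, and it can be closed from existing charts. But the rule governs inclusion in the study as a whole, and no sentence limits it to efficacy.

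Two stronger readings are tempting, and the documents support neither.

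- A reader might link the rule to the generic exclusion, "Subjects not meeting all inclusion criteria", and to the Data Analysis statement "Data will be collected on all patients who meet the inclusion criteria for this study", and infer that leavers' data are never collected. The rule stands under Retention and is not in either inclusion list, so those two sentences do not carry it. The second also goes on to refer to consent, which leans towards all consented eligible patients.
- A reader might infer that the rule biases the BFR versus control comparison. That would need unequal filtering between the groups, which the documents do not show.

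**Conclusion.** The point holds for safety and tolerance. As written, attendance after the start of treatment decides inclusion, the visits are undefined, and neither the safety purpose nor Secondary aim 3 is exempt. Tolerance could be reported as better than it was, provided that the rule is applied to aim 3 and that side effects lower attendance. Patients who stop or struggle with BFR but keep attending are not affected.

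The size cannot be known from the documents. The fall from 21.2% to 13.3% is an illustration on assumed counts, and other assumptions give no bias or the opposite bias. The wording gap is certain; the amount of bias is not. The point does not require removing the rule from the efficacy comparison. It should be fixed before the data set is frozen.

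**What to change.** 1. State that the 90% rule does not apply to safety and tolerance.
2. For every consented patient with at least one BFR session, report side effects, inability to complete sessions, and the numbers who stopped BFR or rehabilitation, with reasons. Use the charting already in the Proposed Protocol.
3. Secure these records before the data set is frozen and de-identified.
4. Define which visits count towards the 90%.
5. If the rule is kept for the efficacy comparison, label that comparison as restricted to adherent patients, report the number excluded in each group, and state whether the rule covers the retrospective controls.

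The cost is protocol wording and a listing from existing charts, with no new visits or measurements. The reported tolerance may be less favourable.

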## Patient Reported Outcomes:

- 1) 4 Patient reported outcome measures will be collected at 5 time points listed below:
  - a) Pre-operative visit
  - b) 3 months post-operative
  - c) Return to sport testing
  - d) 12 month follow up
  - e) 2 year follow-up over phone or email
- 2) Outcome measures completed:
  - a) International Knee Documentation Committee (IKDC)
  - b) Anterior Cruciate Return to Sport after Injury (ACL-RSI)
  - c) Knee Injury and Osteoarthritis Outcome Score (KOOS)
  - d) Marx Activity Rating Scale (MARX)

## **Functional Outcome Definitions/Data Points Collected**

- 1. Demographic information will be collected and outcome measures will include the following:
  - a. Age
  - b. Medical record number
  - c. Date of ACL surgery and related surgeries
  - d. Sex
  - e. Graft Type
  - f. Surgeon
  - g. Sport
  - h. Level of competition in sport
  - i. Weight and Height
  - j. BMI
  - k. Weight bearing precautions (weeks)
  - 1. Limb length (cm): ASIS to superior medial malleolus
  - m. Tegner Scale
- 2. Opened or closed Physis (or skeletal maturity)

3. Data will be collected at five different time points during the rehabilitation process. The current standard of care includes a pre-operative visit, a 3-month assessment visit, and a return to sport visit between 6-9 months post-operative, and a1 year follow up. Additionally, we will collect data a 2 year phone/email follow up to record patient outcomes. These assessments are completed in conjunction with the surgeon's follow up visit. The physical therapist completing the assessment will record the outcomes in a secure Excel data collection form.(or Access data base)

## 4.

## A) Pre-operative visit

- a. Isometric knee extension at 60 degrees on involved and involved side.
  - i. Quadriceps deficit= 100- (Knee extension peak torque involved/knee extension peak torque uninvolved)
- b. Isometric knee flexion at 60 degrees on involved and uninvolved side
  - i. Hamstring Deficit= 100- (Knee flexion peak torque involved/knee flexion peak torque uninvolved)
- c. Isometric hip extension at 60 degrees on involved and uninvolved side
  - i. Hip extension deficit= 100- (Hip extension peak torque involved/hip extension peak torque uninvolved)
- d. Quad hypertrophy will be measured by thigh circumference measurement.
  - i. Measured at 10cm above the superior pole of the patella bilaterally

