### **Introduction**

Anterior cruciate ligament (ACL) injury is a very common injury for adolescents and young adults with over 200,000 ACL injuries reported in the United States each year [1]. The standard treatment for this injury includes ACL reconstruction surgery and physical therapy. Rehabilitation of this surgery requires that adequate quadriceps rehabilitation is important for full return function and activity. The role of quadriceps strength recovery after ACL reconstruction has been well studied and is associated with return to play times, knee kinematics and patient reported outcomes [2]. Paterno et al. reported that patients with greater fear on Tampa Scale of Kinesiophobia (TSK-11) were six times more likely to have a quadriceps LSI of less than 90% supporting the role of adequate quadriceps strength in reduction of risk of sustaining a contralateral ACL injury or re-injury [3]. Ithurburn additionally reported that athletes who demonstrated quadriceps strength asymmetry at time of return to sport (RTS) were likely to demonstrate lower knee related function [4].

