## B) 3 month evaluation:

- e. Isometric knee extension at 60 degrees on involved and involved side.
  - i. Quadriceps deficit= 100- (Knee extension peak torque involved/knee extension peak torque uninvolved)
- f. Isometric knee flexion at 60 degrees on involved and uninvolved side
  - i. Hamstring Deficit= 100- (Knee flexion peak torque involved/knee flexion peak torque uninvolved)
- g. Isometric hip extension at 60 degrees on involved and uninvolved side
  - i. Hip extension deficit= 100- (Hip extension peak torque involved/hip extension peak torque uninvolved)
- h. Quad hypertrophy will be measured by thigh circumference measurement.
  - i. Measured at 10cm above the superior pole of the patella bilaterally.

- i. Y Balance Test (all measures taken bilaterally)
  - i. 3 trials anterior reach involved and uninvolved (cm)
  - ii. 3 trials posteromedial reach involved and uninvolved (cm)
  - iii. 3 trials posterolateral reach involved and uninvolved (cm)
  - iv. Anterior reach difference= Max anterior reach involved Max anterior reach uninvolved
  - v. Posteromedial reach difference= Max posteromedial reach involved- Max posterior reach uninvolved
  - vi. Posterolateral reach difference= Max posterolateral reach involved-Max posterolateral reach uninvolved.
  - vii. Involved and Uninvolved Composite score= (Max anterior reach+ Max posteromedial reach + max posterolateral reach)/(3\*Limb Length) \*100.
- j. 8" Anterior Stepdown Test (measures taken bilaterally)
  - i. Involved repetitions= Max repetitions in 1 minute.
  - ii. Uninvolved repetitions= Max repetitions in 1 minute.
- k. Elevated single leg bridge test completed with a 12" box (all measures taken bilaterally)
  - i. Involved repetitions= Max repetitions in 1 minute.
  - ii. Uninvolved repetitions= Max repetitions in 1 minute.
- 1. Half kneeling dorsiflexion distance (all measures taken bilaterally)
  - i. Half kneeling difference = half kneeling involved- half kneeling non involved

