### 5. Return to sport testing:

- a. Isometric knee extension at 60 degrees on involved and involved side.
  - i. Quadriceps deficit= 100- (Knee extension peak torque involved/knee extension peak torque uninvolved)
- b. Isometric knee flexion at 60 degrees on involved and uninvolved side
  - i. Hamstring Deficit= 100- (Knee flexion peak torque involved/knee flexion peak torque uninvolved)
- c. Isokinetic knee extension at 300 deg/ sec, 180 deg/sec, and 60 deg/ sec
  - i. Quadriceps deficit= 100- (Knee extension peak torque involved/knee extension peak torque uninvolved)

- d. Isokinetic knee flexion 300 deg/ sec, 180 deg/sec, and 60 deg/ sec
  - i. Hamstring Deficit= 100- (Knee flexion peak torque involved/knee flexion peak torque uninvolved)
- e. Isometric hip extension at 60 degrees on involved and uninvolved side
  - i. Hip extension deficit = 100 (hip extension peak torque involved/ hip extension peak torque uninvolved)
- f. Quad hypertrophy will be measured by thigh circumference measurement.
  - i. Measured at 10cm above the superior pole of the patella bilaterally
- g. Anterior reach test (all measures taken bilaterally)
  - i. 3 trials anterior reach involved and uninvolved (cm)
  - ii. Anterior reach difference= Max anterior reach involved Max anterior reach uninvolved
- h. Single leg heel raise testing (all measures taken bilaterally)
  - i. Maximum number of repetitions completed to maximum height at pace of 60 beats per second
  - ii. Heel raise difference = heel raise involved heel raise non involved
- i. 8" Anterior Stepdown Test (measures taken bilaterally)
  - i. Involved repetitions= Max repetitions in 1 minute.
  - ii. Uninvolved repetitions= Max repetitions in 1 minute.
- j. Half kneeling dorsiflexion (all measures taken bilaterally)
  - i. Half kneeling difference = half kneeling involved- half kneeling non involved
- k. Single leg hop for difference (all measures taken bilaterally)
  - i. Single leg hop difference = maximum involved distance maximum non- involved distance
- 1. Timed hop for distance (all measures taken bilaterally)
  - i. Timed hop difference = time involved time non involved
- m. Single leg triple hop for distance (all measures taken bilaterally)
  - i. Single leg triple hop difference = maximum involved distance maximum non-involved distance
- n. Cross over hop for distance (all measures taken bilaterally)

- o. Cross over hop difference = maximum involved distance maximum non-involved distance

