- 6. 12-month testing

Tegner Activity Scale

- 7. Prospective control: All prospective controls will follow the ACL reconstruction protocol at an outside facility. These patients will complete outcome measures, and standardized strength assessments consistent with the standard current standard of care listed above. The same data points will be collected.
- 8. Retrospective controls: Outcome measures (RSI, IKDC) and the results of standardized 3 and 6mo + assessment results will be collected.
- 9. All data points listed above for all three groups will be stored in a Microsoft Excel spreadsheet on the G drive.

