## **Data Collection and Management**

a. Data collection forms: All data will be entered into a Microsoft Excel database to facilitate data analysis.

b. Data collection software: Data collection software will include Microsoft Excel to organize data. Statistics will be run using Microsoft Excel.

c. All outcome measures will be completed and stored in a secure online database: Microsoft Excel spreadsheet on G drive.

d. [name] will oversee data management. The data will be collected by investigators, and it will be stored in a secured folder on the G drive. The spreadsheet will only be accessible to those individuals included in this study.

e. Information will be reviewed prior to de-identification to insure there are no errors with transcription.

f. Data quality assurance: Data that is collected will be manually verified to ensure that no information has been entered into Excel incorrectly. Additionally, we will randomly check 10% of data in the Excel data base for accuracy after initial entry to insure accuracy.

CCMC Department of Research

g. Record retention and confidentiality will be dictated by the current procedures in place here at Connecticut Children's. All information will be stored in a private office and on a single password protected computer. No access to information is possible from an outside source.

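### The strength-deficit formulas leave out the multiplication by 100: as printed, equal limbs score 99 instead of 0, and a limb at 80% of the other side scores 99.2 instead of 20

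*Combined protocol and SAP*

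**What the plan says.** In the combined protocol and SAP, section 4 A (Pre-operative visit) defines the quadriceps deficit as "Quadriceps deficit= 100- (Knee extension peak torque involved/knee extension peak torque uninvolved", after which the bracket closes and the formula ends. The hamstring and hip extension deficits there have the same form. Section B (3 month evaluation) repeats all three, for example "Hamstring Deficit= 100- (Knee flexion peak torque involved/knee flexion peak torque uninvolved". Section 5 (Return to sport testing) has five deficit formulas: isometric knee extension and flexion, isokinetic knee extension and flexion, and hip extension. The hip extension line reads "Hip extension deficit = 100 (hip extension peak torque involved/ hip extension peak torque uninvolved", with no minus sign.

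Two other places show the scale the authors had in mind. The Introduction speaks of patients more likely "to have a quadriceps LSI of less than 90", with a percent sign after the 90. The Y Balance composite in section B begins "Involved and Uninvolved Composite score= (Max anterior reach+ Max posteromedial reach + max posterolateral reach"; it is then divided by three limb lengths and explicitly multiplied by 100.

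On use of the data, Data Analysis says "Descriptive statistics will be completed to help gain an overall understanding of the data for the effect of BFR training" on leg strength, among other outcomes, and plans t-tests and correlations. For prospective controls, item 7 says "The same data points will be collected".

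**The concern.** A percentage deficit should be 0 when the limbs are equal and should rise by one point for each percentage point of strength lost. The printed formula does neither, because it subtracts a number close to 1 from 100. No section restates the deficit correctly or says that the ratio is already a percentage.

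Strength is the subject of primary aim 1. The two isokinetic formulas each cover three speeds, so the eleven lines define 9 + 2 × 3 = 15 deficit values per patient. If the printed rule were applied, the descriptive statistics on deficit would be on a scale that no reader could interpret.

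The checks under Data Collection and Management are aimed mainly at entry and transcription ("Data that is collected will be manually verified to ensure that no information has been entered into Excel incorrectly"), and none is described specifically for derived values.

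**Working it through.** The plan gives no worked deficit value and no power figure based on a deficit, so there is no stated result to reproduce. The check is direct arithmetic on the formula.

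**Inputs.** Let r = involved peak torque / uninvolved peak torque, as in sections 4 A, B and 5. The value r = 0.90 corresponds to the limb symmetry level in the Introduction; the other values of r are illustrative.

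**Formulas.** Printed: f(r) = 100 − r. Intended: g(r) = 100 − 100r.

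| r | Printed, 100 − r | Intended, 100 − 100r |
|---|---|---|
| 0.50 | 99.5 | 50 |
| 0.80 | 99.2 | 20 |
| 0.90 | 99.1 | 10 |
| 1.00 | 99.0 | 0 |

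**Range.** From r = 0.50 to r = 1.00 the printed score moves 99.5 − 99.0 = 0.5 units; the intended score moves 50 − 0 = 50.

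**Inverse check.** The printed score is 0 only if r = 100, that is, if the involved limb is 100 times as strong as the other. It is 20 only if r = 80.

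**Group difference (illustrative).** Mean ratios of 0.80 and 0.70 give |99.2 − 99.3| = 0.1 as printed and |20 − 30| = 10 as intended.

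**Effect on tests.** Substituting r = 100 − f into g gives g = 100 − 100(100 − f) = 100f − 9900. At r = 0.80 this is 9920 − 9900 = 20, as it should be. The relation is linear with a positive slope, so raw differences and standard deviations change by a factor of 100, while t, correlation, p and standardised differences do not change. A simulated two-group comparison (33 and 14 patients; assumed mean ratios 0.80 and 0.72, SD 0.12) gave t = −2.506 and p = 0.0159 on both scales. The sample SD in the larger group was 0.109 on the printed scale and 10.9 on the intended one.

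**Count.** 3 pre-operative + 3 at 3 months + 5 at return to sport = 11 formulas, of which 10 print with the minus sign.

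**The eleventh line.** Read literally, the return-to-sport hip extension formula is 100 × r, giving 100 for equal limbs and 80 at r = 0.80, which is a symmetry index. Minus signs are also missing from neighbouring reach, heel-raise and hop differences, so this is probably an extraction loss and is not counted as a separate error. With the minus sign restored, the line has the same missing factor of 100.

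**The case against.** The strongest reply is that this is shorthand. Subtracting from 100 and calling the result a deficit makes sense only if the ratio is read as a percentage, and the Introduction uses limb symmetry that way. On that reading r = 0.80 gives 20. A score of 99 for equal limbs would probably be noticed, the Excel file in which deficits would be computed is not among the documents reviewed, and Data Collection and Management also plans a random 10% accuracy check that is not expressly limited to raw values. Data Analysis does not say whether deficit or torque is to be tested. Values already computed could be rescaled exactly if stored unrounded, or recomputed from the torques.

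Most of this stands, and it limits the severity. It does not remove the error. The text nowhere says the ratio is a percentage, and the authors wrote out the factor of 100 for the Y Balance composite. That factor survived extraction, so losing the same factor from ten separate lines in extraction is implausible. An outcome definition should not depend on the reader guessing the scale, particularly as de-identified data go to an outside collaborator for analysis.

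One condition deserves attention. Test results are unaffected only if all groups share one scale. Study Design allows previous patients as a fallback comparison, and item 8 takes their existing assessment results. The documents do not say how any deficits in those records were calculated. If they were percentages and the study sheet followed the printed rule, the groups would be on different scales. This is a possibility, not something the documents show.

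**Conclusion.** The concern holds and is minor. Ten formulas are wrong as printed, and the eleventh would be too once its probable minus sign is restored. Confidence is high as to the printed text. The effect on reported results depends on whether the Excel sheet follows the printed rule, which cannot be seen from the documents.

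If it does, deficits between r = 0.50 and r = 1.00 are reported as 99.5 to 99.0 instead of 50 to 0. Provided one scale is used for all groups, no planned test result changes. No eligibility rule, threshold or sample size in the documents uses a deficit value.

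**What to change.** In sections 4 A, B and 5, write every strength deficit as: deficit (%) = 100 − 100 × (involved peak torque / uninvolved peak torque). Check that the Excel sheet uses this formula for the BFR group, the prospective controls and any retrospective controls; equal torques should return 0, and a ratio of 0.80 should return 20.

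The cost is one formula corrected in eleven places and a check of the spreadsheet. No visit, measurement or planned test changes, and no new data are needed.
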